6 STATISTICAL METHODOLOGY

6.1 General Considerations

Continuous data will be summarized descriptively including the number of subjects (n), mean, standard deviation (SD), median, minimum and maximum. Categorical data will be summarized by frequencies and percentages. Percentages by categories will be based on the number of subjects with no missing data, i.e. the percentages for the non-missing categories will add up to 100%.

All statistical comparisons, if applicable, will be conducted using 2-sided tests at the 5% significance level.

All data summarization and analyses will be performed using SAS[®] on Unix. Specifications for table, figures, and data listing formats can be found in the Tables Listings and Figures (TLF) specifications.

6.2 Study Population

In general, data such as patient disposition, demographics and baseline characteristics will be summarized for SAF population.

6.2.1 Disposition of Subjects

Disposition of subjects will be summarized for the SAF by treatment group and overall. Number of subjects who complete or prematurely discontinue from the treatment or study (ie, follow up period) will be summarized by treatment group and overall. For the discontinuation, the primary reason reported by the investigator will be summarized.

Number and percentage of subjects for each analysis set will be summarized by treatment group and overall.

6.2.2 **Protocol Deviations**

The number and percentage of subjects with the following protocol deviation criteria will be summarized for SAF for each criterion and overall, by treatment group and total as well as by investigative site. Subjects deviating from a criterion more than once will be counted once for the corresponding criterion.

The unique identifiers will be as follows:

- PD1 Entered into the study even though they did not satisfy entry criteria,
- PD2 Developed withdrawal criteria during the study and was not withdrawn,

PD3 - Received wrong treatment or incorrect dose,

PD4 - Received excluded concomitant treatment.

The number of subjects who were impacted by COVID-19 will be summarized by impact item and treatment group and overall for SAF population. The impact items include treatment discontinuation, dosing change/interruption, death from COVID-19, healthcare encounter due to COVID-19, protocol deviation due to COVID-19.

An overview listing of subjects who were affected by COVID-19 will be generated by the impact items.

Detailed information on how these assessments are impacted by COVID-19 can be found in relevant data listings with a flag for COVID-19.

6.2.3 Demographic and Other Baseline Characteristics

The Demographics, tobacco history (smoking status), substance use (e-cigarette, alcohol, cannabis), caffeine beverage intake, height and weight, and targeted medical history will be

summarized descriptively by treatment group and total group for SAF. Age group categories include <40 years, \geq 40 years to <46 years, \geq 46 years to <51 years, \geq 51 years to <56 years, \geq 56 years to <61 years, \geq 61 years to <66 years, and \geq 66 years. Hormone replacement therapy history will be summarized descriptively by treatment groupand total group for SAF.

Medical history is coded in MedDRA, and will be summarized by System Organ Class (SOC) and Preferred Term (PT), by treatment group and total group for the SAF.

6.2.4 Previous and Concomitant Medications

Previous and concomitant medications will be summarized by therapeutic subgroup (ATC 2nd level) and chemical subgroup (ATC 4th level) and preferred WHO name by treatment group for the SAF. Subjects taking the same medication multiple times will be counted once per medication and investigational period.

Previous medications are defined as medications that patients started prior to first administration of study medication. Concomitant medications are defined as any medications that patients took after the first dose of study medication and through 30 days from last dose of study drug. Medications that started prior to first administration of study drug and continued while study drug was given will be counted in both previous and concomitant medications.

6.3 Study Drug Exposure and Compliance

Duration and compliance of study drug will be summarized for SAF by treatment group, fezolinetant total and overall.

Number and percentages of subjects with the following categories of study drug duration will be summarized:

- > 0 to ≤ 1 days;
- > 1 to \leq 7 days;
- > 7 to \leq 14 days;
- > 14 to \leq 21 days;
- > 21 to \leq 28 days;
- > 28 to \leq 42 days;
- > 42 to \leq 56 days;
- > 56 to \leq 84 days;
- > 84 to \leq 168 days;
- > 168 to \leq 252 days;
- > 252 to \leq 365 days;
- > 365 days.

Number and percentages of subjects with the following cumulative categories of study drug duration will be summarized:

- ≥ 1 day;
- \geq 7 days;
- \geq 14 days;

- ≥ 21 days;
- ≥ 28 days;
- \geq 42 days;
- \geq 56 days;
- \geq 84 days;
- \geq 168 days;
- \geq 252 days;
- \geq 365 days.

Overall treatment compliance with the dosing schedule will be examined for subjects in the SAF whose total study drug count and first and last days of treatment are known. Compliance will be calculated compared to the actual treatment period of dosing (first to last day of the treatment period), not to the planned treatment period.

Percent overall compliance will be summarized in two ways for the SAF by treatment group, fezolinetant total and overall:

- Descriptive statistics.
- Percent compliance will be categorized according to the following categories:
 - Less than 50%,
 - at least 50%, less than 85%,
 - at least 85%, less than 120%,
 - Over or equal to 120%, and
 - Unknown.

To evaluate impact of the COVID-19 to study drug intake, additional analyses will be performed by excluding the days of missing study drug/drug interruption due to COVID-19 in the duration and compliance calculation, according to the study drug interruption CRF page.

6.4 Analysis of Efficacy

6.4.1 Analysis of Primary Efficacy Endpoint(s)

Not applicable.

6.4.1.1 Primary Analysis for Primary Efficacy Endpoint(s)

Not applicable.

6.4.2 Analysis of Secondary Efficacy Endpoints

Not applicable.

6.4.3 Analysis of Exploratory Endpoints

The exploratory endpoints include the MENQOL and the EQ-5D-5L which will be assessed at baseline and weeks 4, 12, 24 and 52. The exploratory PRO endpoints will be analyzed for the FAS set if not specified. Summary statistics will be provided by treatment group. For analyses by visit, the visit windows from Section 6.10.1 will be applied.

The exploratory PRO variables include the effect of fezolinetant on the following:

- Mean change on the Menopause-Specific Quality of Life (MENQOL) Total Score from baseline to specified time points.
- Mean change on the MENQOL Domain Scores from baseline to specified time points.
- Mean change on the Euro-Qol 5D-5L (EQ-5D-5L) Visual Analog Scale (VAS) from baseline to specified time points.
- Euro-Qol 5D-5L (EQ-5D-5L) domain scores

For the treatment comparison of continuous endpoints, a mixed model for repeated measures (MMRM) will be used. The model will include treatment, visit, and strata smoking status (current vs former/never) as factors, with baseline weight and baseline measurement as covariates, as well as an interaction of treatment by visit and an interaction of baseline measurement by visit. An unstructured covariance structure shared across treatment groups will be used to model the within-patient errors (and then Toeplitz if model does not converge). The Kenward-Roger approximation will be used to estimate denominator degrees of freedom and adjust standard errors. EQ-5D domain scores-will be summarized and analyzed using Cochran Mantel Haenszel (CMH) test with modified ridit scores. EQ-5D will also be adjusted for the baseline score.

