1.3.2 Summary of Clinical Studies

To date, 10 clinical studies have been completed with fezolinetant; 6 phase 1 studies (ESN364-CPK-101, ESN364-CPK-102, ESN364-CPK-103, 2693-CL-0020, 2693-CL-0006 and 2693-CL-009) and 4 phase 2 studies (ESN364-HF-204, ESN364-UF-02, ESN364-PCO-201 and ESN364_HF_205). Two of the 4 phase 2 studies were performed in women with MR-VMS (Studies ESN364_HF_204 and ESN364_HF_205). The 10 completed studies with fezolinetant are shown in [Table 2](#).

The pharmacokinetics of fezolinetant were characterized in studies in healthy subjects and in patients with VMS. After oral intake, fezolinetant showed generally dose proportional pharmacokinetics at doses between 20 and 60 mg once daily in female subjects. Maximum concentration (C_{max}) was generally reached within 1 to 4 hours postdose with terminal half-life ranging between 4-6 hours in healthy subjects and patients. With a once daily dose regimen, steady state plasma concentrations were achieved by approximately day 2 with minimal accumulation. Low plasma protein binding of fezolinetant (50%) was observed with almost equal distribution of fezolinetant into red blood cells and plasma, with a blood-to-plasma ratio of 0.9.

Fezolinetant undergoes extensive metabolism, primarily by cytochrome P450 (CYP) 1A2 enzyme, to form the major metabolite ES259564. A strong CYP1A2 inhibitor (fluvoxamine) increased fezolinetant area under the concentration-time curve (AUC) and C_{max} approximately 9-fold and 1.8-fold, respectively, while smoking was shown to decrease AUC and C_{max} to a geometric least squares mean ratio of 48.3% and 71.7%, respectively (2693-CL-0006).

In a recently completed mass balance study (ESN364_CPK_103), the routes of excretion of fezolinetant were found to be via urine (76.9%) and feces (14.7%). In urine, a mean of 1.1% of the administered fezolinetant dose was excreted unchanged and 61.7% of the administered dose was excreted as metabolite ES259564.

Fezolinetant did not show clinically significant food effects on its pharmacokinetic exposure parameters (ESN364_CPK_101). Based on population pharmacokinetic modeling analyses, body weight was not identified as an important predictor of AUC. However, male subjects are predicted to have 53.2% reduction AUC and 14.9% reduction in C_{max} , compared to females. Asian population was predicted to have a 25% increase in steady-state C_{max} and AUC, which is consistent with clinical observations (Study 2693-CL-0020)

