4.5 Assignment and Allocation

Subjects will be randomized in a 1:1:1 ratio of fezolinetant to placebo to a treatment arm according to the randomization schedules and stratified by smoking status (smoker or non-smoker) through IRT. The site personnel will dispense the treatment according to the IRT system's assignment. Specific procedures for randomization through the IRT are contained in the study procedures manual.

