2.3 Randomization

Subjects will be randomized to receive fezolinetant 45 mg qd, fezolinetant 30 mg qd, or placebo in a blinded fashion such that the investigator, sponsor's study management team, clinical staff, nor the subject will know which agent is being administered. The randomization number will be assigned based on information obtained from the Interactive Response Technology (IRT).

Subjects will be randomized in a 1:1:1 ratio to a treatment arm according to the randomization schedules and stratified by smoking status (current smoker vs former/never) through IRT. The site personnel will dispense the treatment according to the IRT system's assignment. Specific procedures for randomization through the IRT are contained in the IRT specification manual for the study.

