In general, summary statistics will be provided for all the safety parameters. Treatment comparisons will be performed for endometrial and bone density related endpoints. For AESI, the rate, odds ratio and their corresponding 95% exact confidence intervals will be presented, which will be constructed based on Santner-Snell approach. An ANCOVA model, with treatment and strata smoking status (current vs former/never) as factors, with baseline weight and baseline as covariates, will be used for single assessment continuous endpoints. Each following section will specify the analysis method appropriately.

The change and percentage reduction in serum concentrations of sex hormones and sex hormone-binding globulin (SHBG) from baseline to each analysis visit will be summarized.

For hormone related parameters, if the value is below the low limit of quantification, the value will be imputed as half of the LLOQ. In addition, the percentage of subjects who have BLOQ values at baseline who then have measurable post-baseline values will be summarized.

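### The CMH test for the EQ-5D-5L domains names baseline score as its only adjustment and omits smoking status, the sole randomization stratum

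*SAP*

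**What the plan says.** SAP 6.4.3 gives two sentences to the domain scores. They call for a "Cochran Mantel Haenszel (CMH) test with modified ridit scores. EQ-5D will also be adjusted for the baseline score". No further stratum or covariate is named for this test.

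The continuous patient-reported endpoints in the same section (MENQOL scores and the EQ-5D VAS) go into an MMRM: "The model will include treatment, visit, and strata smoking status (current vs former/never) as factors, with baseline weight and baseline measurement as covariates". SAP 6.5 sets the same pattern for continuous safety endpoints assessed once: "An ANCOVA model, with treatment and strata smoking status (current vs former/never) as factors, with baseline weight and baseline as covariates". SAP 6.5.5 (endometrial thickness) and 6.5.6 (BMD and TBS) repeat it, and Protocol 7.5, 7.6 and 7.6.6 carry smoking status in the corresponding models.

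SAP 2.3 says randomization is "stratified by smoking status (current smoker vs former/never) through IRT". Protocol 4.5 says "stratified by smoking status (smoker or non-smoker) through IRT". Neither lists a second factor.

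**The concern.** A CMH test adjusts only through its strata, so the list of strata defines the test. Read literally, SAP 6.4.3 gives five strata (the baseline levels of a domain) and leaves out the one factor the trial randomizes within. The plan's convention elsewhere is to carry that factor into each adjusted model, and it labels it there as a stratum. The VAS and the five domains come from one questionnaire, yet only the VAS analysis would reflect the randomization.

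Two things are at stake, both modest. One is consistency between the randomization and the analysis. The other is pre-specification: two programmers could build different strata from this wording and obtain different p-values. No primary or secondary endpoint, sample-size figure or error-rate claim depends on the test.

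**Working it through.** **1. Does another section supply the stratum?** The plan states no figure for this test, so there is nothing to reproduce, and the question is one of text.

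- The MMRM sentence in SAP 6.4.3 that contains smoking is limited to continuous endpoints.
- SAP 7.1 explains that the domain method was added because the domain scores are categorical and the continuous method does not apply to them. The smoking term therefore cannot be read across.
- Protocol 7.5 describes no CMH test.

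Nothing fills the gap.

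**2. Size of the strata.** Baseline only: 5 levels, so 5 strata. Baseline by smoking: 5 × 2 = 10 strata. If the test is pairwise against placebo (the SAP does not say), 2 × 580 = 1160 women are planned per comparison. That is the number randomized, and fewer may have EQ-5D data at a given visit. The strata will not fill evenly. As an illustration with assumed rates, a domain level held by 1% of women, with 20% smokers, gives 0.01 × 0.20 × 1160 = 2.3 women in that cell.

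**3. Effect on error rate and power.** The documents give no smoking prevalence, domain distribution or treatment effect, so every input except the 580 per arm and the two-sided 5% level is an assumption:

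- smokers 10%, 20% or 30%, with allocation balanced within smoking status;
- smoking shift of 0, 0.3 or 0.8 on a latent scale with SD 1;
- treatment shift of 0 (null) or 0.2 (alternative);
- independent noise of SD 0.8 added at baseline and at follow-up, so the latent correlation between them is 1/(1 + 0.8²) = 0.61;
- five ordered levels from cut points 0.3, 1.1, 1.8 and 2.4;
- 2000 runs per scenario.

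Within stratum k of size N_k, the modified ridit is r = rank/(N_k + 1). With n_1k treated women and stratum mean r̄_k, the statistic is

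Q = [Σ_k (sum of treated ridits − n_1k r̄_k)]² / Σ_k [n_1k (N_k − n_1k) / (N_k (N_k − 1)) × Σ_i (r_ik − r̄_k)²],

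referred to chi-square on 1 df. A stratum with one arm empty is skipped.

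| Smokers | Smoking shift | Type I, baseline only | Type I, baseline × smoking | Power, baseline only | Power, baseline × smoking |
|---|---|---|---|---|---|
| 10% | 0 | 4.50% | 4.85% | 72.85% | 72.60% |
| 10% | 0.3 | 4.65% | 5.15% | 74.70% | 74.20% |
| 10% | 0.8 | 4.75% | 4.95% | 74.30% | 73.95% |
| 20% | 0 | 4.75% | 4.85% | 71.65% | 71.55% |
| 20% | 0.3 | 4.25% | 4.60% | 74.70% | 74.10% |
| 20% | 0.8 | 4.45% | 4.25% | 76.10% | 75.60% |
| 30% | 0 | 5.70% | 5.65% | 74.30% | 74.30% |
| 30% | 0.3 | 4.85% | 4.95% | 73.80% | 73.80% |
| 30% | 0.8 | 4.70% | 4.75% | 75.50% | 75.85% |

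The Monte Carlo standard error of one type I entry is √(0.05 × 0.95/2000) = 0.49 points, so all entries are compatible with 5%. The largest power difference is 74.70 − 74.10 = 0.60 points, and it favors baseline only. The one gain from adding smoking is 75.85 − 75.50 = 0.35 points, with 30% smokers and the largest shift. A further simulation over the same smoking ranges, with baseline correlation 0.3 or 0.6, agreed: type I error near 5% either way, power within about 1 point, and a gain only when smoking strongly predicts the outcome.

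Stratifying by smoking alone gave power of 59.75% to 62.15%. Under these inputs the baseline score, which the plan does name, does most of the work.

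**The case against.** The strongest reply is that nothing is lost. The simulated error rate does not move, power differs by less than a point and usually in the other direction, and the endpoint is exploratory. This stands. A reader might infer that leaving out the stratum makes these p-values materially conservative or costs real precision. The documents give no association between smoking and the domains, and the assumed ranges show no such cost.

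A reader might also argue that smoking matters because "smoking was shown to decrease AUC" (Protocol 1.3.2, geometric mean ratio 48.3%). That does not support the point. It concerns drug exposure, so it bears on whether the treatment effect differs in smokers. It does not show that smoking predicts EQ-5D responses, and a stratified CMH test would not report such a difference.

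Third, the word *also* in the baseline sentence may mean that baseline is added to an unstated smoking stratum. This is possible, so a deliberate decision to drop smoking cannot be inferred. It does not close the gap, because the strata are still not written down.

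Finally, adding smoking does not make the domain and VAS analyses identical: the MMRM also has baseline weight and visit interactions. Thin cells are also a genuine, if small, drawback. Both points stand. The first limits the consistency claim to the randomization factor, and the second is why the fix needs a pooling rule.

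**Conclusion.** The point holds as a minor one. As written, the CMH test for the EQ-5D-5L domains adjusts for baseline score only and omits the sole randomization stratum, which every MMRM and ANCOVA in the plan includes. The text leaves the intent open, and no other section settles it.

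The size is very small: type I error near 5% either way and a power change of about 1 point or less. This rests on assumed smoking prevalence, smoking effect, baseline correlation and treatment effect, on complete data in 580 women per arm, and on pairwise comparison with placebo. The reason to act is that the analysis should follow the randomization, with at most a slight gain in precision.

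**What to change.** In SAP 6.4.3, replace the description of the domain test with:

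> CMH test with modified ridit scores, stratified by randomization smoking status (current vs former/never) and baseline domain level, with adjacent sparse baseline levels pooled by a rule set before unblinding.

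The cost is one sentence, one more stratum variable in the program and a short pooling rule. The small downside is that a thin smoking-by-baseline cell with one arm empty drops out of the test; the pooling rule addresses that. If smoking was left out on purpose, a sentence giving the reason would remove the ambiguity.

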6.5 Analysis of Safety

Overall long-term safety of fezolinetant and the effect of fezolinetant on endometrial health will be the primary objective of this study. The safety assessments include adverse events, laboratory assessments, vital signs, C-SSRS, ECG, endometrial health assessment and imaging (mammogram, DXA, TVU). In all analysis of safety, the treatment group includes placebo, fezolinetant 30mg, fezolinetant 45mg and fezolinetant total will be presented by treatment group for SAF, unless specified otherwise. For analyses by visit, the analysis windows from Section 6.10.1 will be applied. Except for adverse events and follow-up visit data, only data up to one day after the last dose date will be considered for the analyses.

The baseline value for safety endpoint will be the last non-missing value taken on or prior to first dose of study drug unless otherwise noted.

Primary Safety Variables

- Frequency and severity of AEs.
- Percentage of subjects with endometrial hyperplasia.
- Percentage of subjects with endometrial cancer.

Secondary Safety Variables

- Change from baseline in endometrial thickness at 12 months.
- Percentage of subjects with disordered proliferative endometrium.
- Change from baseline in bone mass density (BMD) and trabecular bone score (TBS) at hip and spine at 12 months.
- Change from baseline to each timepoint in vital signs: sitting systolic and diastolic blood pressure and pulse rate.

- Change from baseline to each timepoint in laboratory tests: hematology, biochemistry and urinalysis.
- C-SSRS at each timepoint.
- Change from baseline to each timepoint in ECG parameters

Exploratory Safety Variables

- Change from baseline to specified time points in serum concentrations of sex hormones and sex hormone-binding globulin (SHBG) (week 4, 12, 24, 52 and 55).
- Plasma concentration of fezolinetant and the fezolinetant metabolite ESN259564 at specified timepoints (week 4, 12, 24 and 52).

In general, summary statistics will be provided for all the safety parameters. Treatment comparisons will be performed for endometrial and bone density related endpoints. For AESI, the rate, odds ratio and their corresponding 95% exact confidence intervals will be presented, which will be constructed based on Santner-Snell approach. An ANCOVA model, with treatment and strata smoking status (current vs former/never) as factors, with baseline weight and baseline as covariates, will be used for single assessment continuous endpoints. Each following section will specify the analysis method appropriately.

The change and percentage reduction in serum concentrations of sex hormones and sex hormone-binding globulin (SHBG) from baseline to each analysis visit will be summarized.

For hormone related parameters, if the value is below the low limit of quantification, the value will be imputed as half of the LLOQ. In addition, the percentage of subjects who have BLOQ values at baseline who then have measurable post-baseline values will be summarized.

